6.13 CONCOMITANT MEDICATION ASSESSMENTS

All concomitant medications (over-the-counter and prescribed) taken by subjects will be recorded in the CRF with indication, start date/time, and stop date/time, if known.

Subjects are permitted oral disease-specific PAH therapy consisting of an ERA and/or a PDE5-I or sGC stimulator, but not all 3. The on-study addition/substitution of an ERA, PDE5-I or sGC stimulator, if on a single such agent at Baseline, or dosage increase for such agents is permitted. In addition to ralinepag, subjects can be prescribed no more than 1 agent from the ERA class and 1 from the PDE5-I/sGC stimulator class at any 1 time. Substitution and dose adjustment within each of these classes is permitted. Subjects should be evaluated for the presence of clinical worsening if additional therapy or dose adjustments of current therapies are required.

In addition, the following therapies, which may affect PAH, are permitted and may be adjusted in dose as needed:

- Vasodilators (including calcium channel blockers)
- Digoxin
- Spironolactone
- L-Arginine supplementation

Diuretics may be dosed as clinically indicated throughout the study.

Subjects who require treatment with a prostacyclin/prostacyclin analogue (IV, SC, oral, or inhaled), except for acute vasodilator testing during cardiac catheterization, will be discontinued from the study.

6.14 REMOVAL OF SUBJECTS FROM THE STUDY OR STUDY DRUG

Subjects will be allowed to remain on study drug until marketing approval of ralinepag is granted or until the Sponsor discontinues the study. The study will be terminated early if, in the opinion of the Sponsor, Investigator, or IRB/IEC, an unacceptable risk to the safety and welfare of subjects is posed by the continuation of the study in light of review of the key safety data.

Subjects will be informed that they are free to withdraw from the study at any time for any reason should they so wish. The Investigator may remove a subject if, in his/her opinion, it is in the best interest of the subject. A subject may be withdrawn from the study for any of the following reasons:

- Clinical worsening, as defined in Section 6.9
- Deviation/noncompliance with the protocol
- A serious or intolerable AE occurs
- The Sponsor or Investigator terminates the study
- Withdrawal of consent - any subject may withdraw his/her consent from the study at any time. The Investigator should make a reasonable attempt to document the specific reason why consent is withdrawn.

6.14.1 Handling of Withdrawals

Although a subject is not obliged to give his/her reason for withdrawing prematurely, the Investigator will make a reasonable effort to obtain the reason while fully respecting the subject's rights. If there is a medical reason for discontinuation, the subject will remain under the supervision of the study physician until in satisfactory health. Reasonable efforts will be made to contact a subject who fails to attend any follow-up appointments, in order to ensure that he/she is in satisfactory health.

If a subject is prematurely discontinued from this study, every attempt will be made to follow the End of Study Procedures described in Section 7.

In addition, all subjects will be contacted at the time of Study APD811-007 closure to assess vital (mortality) status. The vital status follow-up contact of subjects will depend on local regulations or specific agreement with the subject and Investigator.

6.15 ALLOWABLE VISIT AND PROCEDURE WINDOWS

A ± 3 -day window is allowed for study visits and procedures during the Dose Titration Period, Treatment Period, and End of Study and Follow-up Visits, with the exception of the Q3 Month Visits during the Treatment Period, which are allowed a ± 5 -day window.

7 STUDY ACTIVITIES

7.1 SCREENING VISIT

Given that this study serves as an extension to Study APD811-003, an independent Screening Visit is not required. In order for subjects to be eligible for this study, they must have completed Study APD811-003 as planned or have been assigned to placebo and discontinued for clinical worsening and fulfill the eligibility criteria outlined in Section 4.

Subjects who have an interest in participating in this study should be properly consented prior to completing the Week 25 Visit in Study APD811-003. This is to include a detailed oral presentation of the nature, purpose, risks, and requirements of the study in addition to receiving detailed written information. Each subject should have adequate opportunity to ask the appropriate person of the clinical staff (ie, Investigator or designee) presenting the study about any aspect of the study. Once the subject is satisfied that he/she is willing to participate in the study, he/she will be asked to sign the study ICF. The clinical personnel obtaining written consent from the subject will also sign the form to confirm consent has been obtained. Once signed, the Investigator will retain the original for the subject's study records and provide the subject with a signed copy. The Investigator will verify that informed consent has been obtained from each subject prior to admission into the study and prior to the subject undergoing any study-related procedures. If it is standard practice at the site to conduct a few general noninvasive study procedures (ie, medical/social history, collection of concomitant

medications, etc) before a subject can be considered for a specific study, the study center must have a written SOP detailing the procedure, and also ensure that each subject signs a general consent prior to undergoing the general procedures.

7.2 STUDY PROCEDURES

7.2.1 *Baseline Study Procedures – All Subjects*

Subjects who meet all the entry criteria and are eligible for the study will report to the clinical study unit to confirm eligibility for the study and complete all Baseline procedures and receive study drug and instructions. The study drug will be given in the morning at the study site during the Baseline Visit.

7.2.1.1 *Pre-baseline Procedures*

All Week 25 measurements from Study APD811-003 will serve as Baseline assessments for Study APD811-007.

Placebo-treated subjects who discontinued prematurely from Study APD811-003 due to clinical worsening are permitted to enroll in APD811-007 provided that all end of study procedures are performed per the ADP811-003 protocol. For these subjects, the time of the clinical worsening event that led to early termination in Study APD811-003 will serve as the Baseline time point for clinical worsening in APD811-007.

Any unresolved AE from Study APD811-003 will be carried forward and recorded.

7.2.1.2 *Baseline Procedures*

- Medical history (partial history, to update findings from Study APD811-003)
- Physical exam¹
- 12-lead ECG¹
- Clinical laboratory tests (to include hematology, coagulation parameters, serum chemistry, and urinalysis)¹
- Serum pregnancy test (women only)¹
- Vital signs¹
- 6MWT¹
- BNP/NT-proBNP¹
- Assessment of clinical worsening

- WHO/NYHA FC assessment¹
- Record AEs¹
- Record concomitant medications¹

¹ Taken from Week 25 Visit in Study APD811-003

7.2.2 Study Procedures – for Immediate-release Dose Titration Period (Study APD811-003 Placebo Subjects)

Visits after Baseline should occur weekly for each escalation of study drug dose. There should be 1 study visit per week during the Dose Titration Period. Beyond the weekly visit, any additional visit during the Dose Titration Period will be documented as an ‘unscheduled’ visit.

If a subject reaches a stable MTD and no further dose escalations are planned, the Dose Titration Period will be considered completed and will be followed by monthly assessments for the first 3 months and then every 3 months until the subject is discontinued from the study, Sponsor termination of the study, or the last subject enrolled completes approximately 6 months of treatment with ralinepag.

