 - ^k After the last subject enrolled in Study APD811-007 completes approximately 6 months of treatment and a cumulative all-subject data analysis is performed, as outlined in Section 9 (Planned Statistical Methods), pro-BNP and NT-proBNP testing will subsequently be conducted locally at the discretion of the Investigator (as clinically indicated) during the Q3 monthly visits. Locally collected values will be entered into the Sponsor's clinical database along with the reference ranges.
 - ^l At 1 year (± 3 months) after the subject enrolls into Study APD811-007, an RHC assessment will be conducted. If the subject has been in Study APD811-007 beyond 1 year (± 3 months) at the time of regulatory/ethics approval of this amendment, an RHC assessment will be conducted at 2 years (± 3 months) instead. If a subject has been enrolled in Study APD811-007 more than 2 years at the time of regulatory/ethics approval of Amendment #02, an RHC will be performed at the time of those approvals.

Table 2 Schedule of Procedures and Visits: Study APD811-003 Subjects treated with Placebo entering Study APD811-007

Evaluation ^a	Baseline ^b (APD811-003 Follow-up Visit)	Dose Titration Period									Treatment Period			End of Study (EOS)	28-Day Follow- Up ^c
		9-Week Period									M1-M3	Q3 Months	1 or 2 Years		
		1	2	3	4	5	6	7	8	9	±3 days	±5 days	±3 months		
Informed consent	X														
Medical history	X														
Physical exam	X													X	
ECG (12-lead) ^d	X	X	X	X	X	X	X	X	X	X	X	X		X	
Clinical laboratory tests ^e	X		X			X				X	X	X		X	
Serum pregnancy test ^f	X					X					X	X		X	
Vital signs ^g	X	X	X	X	X	X	X	X	X	X	X	X		X	
Study drug administration		X	X	X	X	X	X	X	X	X	X	X			
6MWT ^h	X										X	X		X	
BNP/NT-proBNP ^k	X											X			
WHO/NYHA functional class assessment ⁱ	X	X	X	X	X	X	X	X	X	X	X	X		X	X
Assessment for clinical worsening	X	X	X	X	X	X	X	X	X	X	X	X		X	X
RHC ^l													X		
Dose escalation/de-escalation assessment												X ^j			
Adverse event monitoring	X	X	X	X	X	X	X	X	X	X	X	X		X	X
Concomitant medication monitoring	X	X	X	X	X	X	X	X	X	X	X	X		X	X

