6.9 ASSESSMENT OF CLINICAL WORSENING

The Investigator will evaluate the subject for potential clinical worsening throughout the study. If clinical worsening is suspected, additional clinic evaluations may be required to make a final determination as to whether clinical worsening has been met. Clinical worsening is defined as fulfillment of any 1 of the following criteria (as assessed by change from baseline in Study APD811-003):

- Death, or onset of treatment-emergent AE (TEAE) with a fatal outcome occurring less than or equal to 14 days after study treatment discontinuation
- Hospitalization for worsening PAH, heart-lung or lung transplant, or atrial septostomy
- The subject requires the addition (or change in dose if applicable) of any of the following PAH specific medications:
 - Prostacyclin/prostacyclin analogue (IV, SC, oral, or inhaled)
 - PDE5-I or sGC
 - ERA
- The combined occurrence of the events listed below:
 - A decrease in 6MWD by at least 20% from baseline, confirmed on two 6MWTs on different days
 - Increase (worsening) in WHO/NYHA FC from baseline
 - Appearance of or worsening of signs/symptoms of right heart failure that did not respond to optimized oral diuretic therapy

In cases of clinical deterioration, the Investigator must assess carefully if the deterioration of the subject's condition (eg, worsening FC) is related to the underlying PH or can be explained by an alternative cause (eg, transient infection, musculoskeletal disease, surgical or medical intervention other than PH related, exacerbation of a concomitant lung disease, lacking compliance of medication intake). Only persistent clinical deteriorations caused by the underlying PAH and confirmed as per the above criteria will be considered clinical worsening.

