8.4 ASSESSMENT WINDOWS

For efficacy and safety assessments, baseline is defined as the last measurement prior to the first dose of ralinepag in the APD811-007 study.

Summary analyses will usually be based on the scheduled (nominal) visits with no visit windows applied. If appropriate, hemodynamic parameters will only be summarized by the Baseline and post-Baseline Visits of APD811-007.

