10 EFFICACY ANALYSES

10.1 TIME TO CLINICAL WORSENING

Time to the first event of clinical worsening will be calculated and listed. Time to clinical worsening is calculated from the treatment start date in APD811-007 to the first occurrence of clinical worsening. For subjects who do not experience clinical worsening, it will be censored at the last record date of clinical worsening assessment or end of study, whichever is latest.

Summaries and analyses will be performed for time to clinical worsening. Kaplan-Meier estimate will be provided along with the corresponding p-value using log-rank test. In addition, hazard ratio, 95% confidence interval, and p-value will be provided using the Cox proportional hazard model. A Kaplan-Meier plot will also be provided.

10.2 6-MINUTE WALK TEST

The listing of the 6MWT will be organized by treatment group in the parent study, and will include the subject number, visit, assessment date/time (day), last ralinepag dose date/time (day), the last ralinepag dose (micrograms), hours from last ralinepag dose to 6MWT, 6MWD results, and use of supplemental oxygen. The summaries of 6MWD will be provided by treatment group in the parent study for each visit. The summaries will include descriptive statistics for 6MWD and the change from baseline. Baseline is defined as the last 6MWD measured prior to the first dose of ralinepag in the APD811-007 study.

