12 CHANGES FROM ANALYSIS PLANNED IN THE PROTOCOL

For the final analysis, the following changes have been made to the analyses that are described in the protocol:

- Safety Population will be used for all summaries (protocol Section 9.1 specifies modified Intent-to-Treat Population for efficacy analyses).
- The protocol separated the primary objective and secondary objectives. The analyses will be based on efficacy and safety, not specifically separating the primary and secondary objectives.
- Protocol Section 6.2 states medical and social history would be updated at Baseline in Study APD811-007. These updates were not collected.
- No imputation will be performed for missing efficacy values (protocol Section 9.1 specifies Last Observation Carried Forward imputation for efficacy missing values).
- Baseline for change from baseline in efficacy values will be the APD811-007 baseline value (protocol Section 9.2 specifies the Day 1 pre-dose measurement in Study APD811-003 as the main baseline, with Day 1 of Study APD811-007 as baseline for a secondary analysis).
- Follow-up vital status (mortality) was not collected.
- Local results of BNP/NT-proBNP are not available.

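### For placebo subjects admitted after worsening in APD811-003, the documents conflict on the reference for clinical worsening, and under one reading deterioration that predates ralinepag can count as an event

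*Protocol*

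**What the plan says.** - **Who enters.** Protocol 4.2 admits placebo subjects who worsened in APD811-003 once their end-of-study procedures are done and their parent-study data are locked. The synopsis excludes ralinepag subjects withdrawn for worsening, and Protocol 4.3 makes its only exception for placebo subjects.
- **Event criteria, Protocol 6.9.** The criteria are judged "as assessed by change from baseline in Study APD811-003", with no exception for prior worseners. The combined criterion needs three things together: "A decrease in 6MWD by at least 20% from baseline, confirmed on two 6MWTs on different days", a worse functional class, and right heart failure not controlled by oral diuretics. It adds: "Only persistent clinical deteriorations caused by the underlying PAH and confirmed as per the above criteria will be considered clinical worsening".
- **Special rule, Protocol 7.2.1.1.** For these subjects the time of the parent-study worsening event "will serve as the Baseline time point for clinical worsening in APD811-007".
- **Schedule.** Table 2 marks the row "Assessment for clinical worsening" at Baseline. Protocol 7.2.1.2 lists that assessment without the footnote for items taken from the parent study's Week 25 visit. The Baseline walk test does carry the footnote. Table 2 schedules no walk during titration; the next is in M1-M3.
- **Clock, SAP 10.1.** "Time to clinical worsening is calculated from the treatment start date in APD811-007 to the first occurrence of clinical worsening". A log-rank test, a Cox hazard ratio and a Kaplan-Meier plot follow. Figure 14.2.1 is by parent-study treatment group.
- **Baseline, SAP 8.4.** For efficacy and safety assessments, "baseline is defined as the last measurement prior to the first dose of ralinepag in the APD811-007 study". SAP 2.2 lists clinical worsening among the efficacy assessments.
- **Declared changes, SAP Section 12.** "Baseline for change from baseline in efficacy values will be the APD811-007 baseline value", set against protocol Section 9.2. Neither 6.9 nor 7.2.1.1 is mentioned.

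**The concern.** These subjects have, by definition, already deteriorated from their APD811-003 baseline. If that baseline remains their reference, a deterioration carried over from the parent study can meet the definition again in the extension, before ralinepag has had a chance to act. SAP 10.1 has no rule that onset must follow the first APD811-007 dose. By contrast, SAP 11.1 does deal with onset for adverse events and identifies those ongoing from the parent study.

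The exposure is one-sided. Ralinepag subjects who worsened in the parent study cannot enter, so any carried-over event falls in the parent-placebo group. The between-group comparison would then credit earlier ralinepag with a difference that arose before the extension began, and overall incidence would include parent-study deterioration.

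**Working it through.** The plan gives no event count, group size or power figure for this endpoint, so there is no figure of its own to reproduce. The check sets the passages side by side, then illustrates size on stated assumptions.

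**1. The references compared**

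| Source | Date used | Kind of reference |
|---|---|---|
| Protocol 6.9 | APD811-003 baseline | Measurement baseline |
| Protocol 7.2.1.1 | Parent-study worsening event | Not stated; could be either |
| SAP 10.1 | APD811-007 treatment start | Time origin |
| SAP 8.4 | Last value before first APD811-007 dose | Measurement baseline; reach over the 6.9 criteria not stated |

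A measurement baseline and a time origin may properly differ, so 6.9 and SAP 10.1 do not conflict merely because their dates do. The conflicts are these:
- 6.9 against SAP 8.4, if 8.4 reaches the event criteria.
- 7.2.1.1 against 6.9, if 7.2.1.1 is a measurement baseline.
- 7.2.1.1 against SAP 10.1, if 7.2.1.1 is a time origin. The parent event precedes the first APD811-007 dose, because 4.2 requires completed procedures and locked data first. Starting there would add event-free time by design.

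**2. When a carried-over event could be recorded under 6.9**

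The walk component needs two tests on different days, and the Baseline walk is itself a parent-study test. A Day 1 event therefore requires parent-study walks to be accepted as the confirming tests. Otherwise scheduled walks can supply confirmation only from M1-M3. SAP Section 8 computes study day as assessment date minus first-dose date; on the same subtraction, an event on the first-dose date has time 0.

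**3. Walk threshold under each reference**

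Threshold as a share of the APD811-003 baseline walk = 0.80 × reference value.
- Against the APD811-003 baseline: 0.80 × 100% = 80%. A subject at 80% already meets this component.
- Against an entry value of 80%: 0.80 × 80% = 64%, a total fall of 36%.
- Against an entry value of 75%: 0.80 × 75% = 60%.

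**4. Effect on the Kaplan-Meier curve**

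Drop at time 0 per event = 1/N, where N is the parent-placebo group size (assumed).
- N = 15: 1/15 = 6.7 points.
- N = 20: 1/20 = 5.0 points.
- N = 25: 1/25 = 4.0 points.

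**5. Effect on the hazard ratio (illustration)**

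Simulation with a true hazard ratio of 1, exponential event times, uniform censoring between 1 and 4 years, Breslow ties and 400 runs per setting. Group sizes, event rates and the number of time-zero placebo events are all assumed. Entries are median hazard ratios, ralinepag to placebo.

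| Ralinepag : placebo | Events per year | 0 at time zero | 1 | 2 |
|---|---|---|---|---|
| 40 : 20 | 0.10 | 1.02 | 0.81 | 0.68 |
| 40 : 20 | 0.20 | 0.99 | 0.89 | 0.80 |
| 30 : 30 | 0.10 | 0.98 | 0.87 | 0.77 |
| 30 : 30 | 0.20 | 1.02 | 0.95 | 0.83 |

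One such event moves the median to 0.81-0.95, and two move it to 0.68-0.83.

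**The case against.** The strongest reply is that the SAP already answers the question. Section 8.4 sets a pre-dose APD811-007 baseline for efficacy assessments, Section 2.2 counts clinical worsening as one, and Section 12 declares the move to that baseline. Read with SAP 10.1, this gives entry values as the reference and the first dose as the clock, and no Day 1 event arises. Nor does one arise if 7.2.1.1 is a measurement baseline that overrides 6.9.

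Much of this stands: the SAP is not silent on reference values. It does not settle the matter, though. Under 6.9 the investigator decides whether worsening has occurred, and SAP 10.1 takes the first occurrence. Nothing tells the analyst to re-judge those decisions against entry values, and the Section 12 item is worded for change-from-baseline values and tied to protocol 9.2. The persistence condition in 6.9 does not exclude deterioration carried over from the parent study.

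Two further points also stand. Only subjects still meeting all three components at entry are exposed; a parent-study hospitalisation or medication change is a past event that does not recur on Day 1. And the consequence is limited: protocol Section 9.2 makes safety the primary analysis and efficacy secondary.

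**Conclusion.** The conflict is real and should be resolved, but it is an ambiguity that permits a biased count, not a plan that necessarily produces one. If 6.9 governs, a subject still meeting the combined criterion can be an event at or soon after entry, in the parent-placebo group only. The Kaplan-Meier, log-rank and Cox comparison would then be biased towards the parent-ralinepag group, by 1/N on the placebo curve for each event at time zero: about 4 to 7 points for an assumed N of 15 to 25. The hazard ratios above rest wholly on assumed inputs and show only that one or two such events matter in a study of about 60 subjects.

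A reader might infer that prior worseners will all be Day 1 events. The documents do not support that: it needs 6.9 to override the other rules, all three components to persist, and parent-study walks to serve as confirmation. A reader might also multiply 1/N by the number of prior worseners; 3 of 15 would give 20 points. That uses the wrong numerator, because only those still meeting the combined criterion count. The documents give neither number, and the relevant one may be zero.

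**What to change.** In SAP 10.1:
- Keep the clock at the first APD811-007 dose for all subjects.
- Count only worsening with onset after that dose.
- State that, for placebo subjects admitted after parent-study worsening, the walk, functional class and right heart failure components are judged against the value at APD811-007 entry, consistent with SAP 8.4.
- Report the clinical worsening analysis with and without these subjects, and state how many there are.

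List the departure from Protocol 6.9 and 7.2.1.1 in SAP Section 12, and reconcile those two protocol passages. The change concerns how events are counted, not how subjects are managed.

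The cost is SAP wording, one additional run, and possibly a re-review of component data for a few subjects. There is a statistical cost too. Resetting the reference makes a further event harder to reach: a subject entering at 80% of the APD811-003 walk must fall to 64% of it, and a subject already in class IV cannot worsen in class. That leans towards the parent-placebo group, which is why the analysis without these subjects is needed alongside.
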